**The Psychopathological Impact of the SARS-CoV-2 Epidemic on Subjects Suffering From
Mental Disorders: Data From ASST Monza**

The Impact of the COVID-19 (SARS-CoV-2 Disease) on Psychopathology

NCT04694482

Document date: **20/04/2021**

STUDY PROTOCOL

Study design and participants

This is an observational retrospective study involving subjects evaluated at three time points: T0, corresponding to the outbreak of the pandemic (January-February 2020); T1, that was the lockdown period (the so-called “phase I”, in March-April 2020); T2, corresponding to the reopening and restarting (the so-called “phase II”, in May-June 2020).

Outpatients (aged 18-65) were recruited at three mental health services of ASST Monza: Cesano Maderno, Monza and Brugherio. Subjects were interviewed during psychiatric visits from November 12th 2020 until January 31st 2020 and information were collected retrospectively for the purposes of the study.

Inclusion criteria for both patients and HC consisted of: (1) being 18-65 years old; (2) ability to comprehend the Italian language; (3) ability to understand and sign the written informed consent. An additional inclusion criterion for patients was having a diagnosis of SKZ, BD, major depressive disorder (MDD), anxiety disorders, OCD or PDs according to the Diagnostic and Statistical Manual of Mental Disorders – 5th edition (DSM 5 – APA, 2013) criteria. An additional inclusion criterion for HC was living in the same geographical area of patients.

Exclusion criteria (for both patients and HC) were: (1) severe mental retardation; (2) pregnancy or post-partum; (3) presence of medical conditions potentially contributing to psychiatric symptoms (e.g. multiple sclerosis or re-exacerbation of inflammatory diseases); (4) treatment with compounds potentially involved in the onset or worsening of psychiatric symptoms (e.g. corticosteroids); (5) being health care workers involved in the sanitary emergency. Moreover, relatives of patients were excluded as HC.

All participants signed informed consent after the nature of the procedures had been fully explained. Study procedures were reviewed and approved by the local accredited Medical Ethics

Review Committee (named “Brianza Ethic Committee”). The research project is conformed to the provisions of the latest version of the Declaration of Helsinki.

Assessment

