Data were collected retrospectively from patients’ medical records or, in case they were lacking, by interviews to the patients or their relatives and caregivers. HC were asked to compile a questionnaire to collect the same data as patients. Information included demographic variables such as age, sex, educational level, occupational status and marital status, as well as clinical variables, such as family history of psychiatric disorders, lifetime substance misuse, substance poly-abuse 6 months before and 6 months after the pandemic, medical (co)-morbidity, medical poly-comorbidity, the presence of at least 2 COVID symptoms, and, for patients, diagnosis. The rating scales are routinely administered during patients’ visits.

Primary outcomes

- Brief Psychiatry Rating Scale (BPRS) at T0, T1, T2;
- Clinical Global Impression (CGI) severity subscale at T0, T1, T2; improvement subscale at T1 and T2;
- Hamilton Anxiety Rating Scale (HAM-A) at T0, T1, T2;
- Impact of Event Scale – Revised (IES-R) at T1 and T2.

These rating scales were administered to all patients. HC were asked to retrospectively fill in the IES-R items referring to T1 and T2.

Secondary outcomes

- Disability Scale (DISS) at T0, T1, T2;
- Positive and Negative Symptoms Scale (PANSS), collected for SKZ patients at T0, T1, T2;
- Hamilton Depression Rating Scale (HAM-D) and Montgomery and Åsberg Depression Rating

Scale (MADRS), collected for MDD and BD patients at T0, T1, T2;

- Young Mania Rating Scale (YMRS), collected for BD patients at T0, T1, T2;
- Yale-Brown Obsessive-Compulsive Scale (Y-BOCS), collected for OCD patients at T0, T1, T2.

STATISTICAL ANALYSIS PLAN

Descriptive analyses of the entire sample were performed. Patients were divided into 5 groups according to diagnosis (SKZ, BD, MDD, anxiety disorders or OCD, PDs); multivariate analyses of variance (MANOVAs) and chi-square tests were used to compare groups on quantitative and qualitative variables respectively.

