Linear regression models, adjusted for repeated measures, were applied to examine whether the change over time in psychometric scores differed between diagnostic groups and, for IES-R, between patients and HC. In the models, psychometric scores were treated as dependent variables. The model included fixed effects of time and diagnosis. The Akaike information criterion (AIC) was used to select the appropriate statistical model. The unstructured variance-covariance matrix was used to account for repeated measures within each subject. The significance was set at $p < 0.05$.

Statistical Package for Social Sciences (SPSS) for Windows (version 26.0) was used as statistical program.

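### The stated model omits recruiting service, so confounding of the diagnostic contrasts by service cannot be excluded

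*Combined protocol and SAP*

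**What the plan says.** Under Study design and participants, the protocol describes a retrospective observational study and states: "Outpatients (aged 18-65) were recruited at three mental health services of ASST Monza: Cesano Maderno, Monza and Brugherio".

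Under Assessment, patient data come from medical records or, where these were lacking, from interviews with patients, relatives or caregivers. On the scales, "The rating scales are routinely administered during" patients' visits. No rater training or agreement procedure is described. The variables given as examples of what was collected do not include service.

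The Statistical Analysis Plan forms five diagnostic groups. Its repeated-measures models are meant to "examine whether the change over time in psychometric scores differed between diagnostic groups and, for IES-R, between patients and HC". On the terms: "The model included fixed effects of time and diagnosis". On selection: "The Akaike information criterion (AIC) was used to select the appropriate statistical model", with no candidate models listed. On correlation: "The unstructured variance-covariance matrix was used to account for repeated measures within each subject".

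Service is not named anywhere as a covariate, random effect, stratum or sensitivity analysis.

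**The concern.** The main comparison is between diagnostic groups that were not formed by randomisation. If one diagnosis was seen mostly at one service and another diagnosis mostly at another, a contrast between the two is partly a contrast between services. Ratings come from routine practice, so services could differ in how severely they score. They could also differ in how scores moved, or in how complete the records were, between T0 and T2. The stated model would attribute either kind of difference to diagnosis, to the extent that the service mix differs between diagnoses. The unstructured covariance does not help, because it deals with correlation within a subject and not with differences between services.

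The two kinds of difference put different results at risk. A stable one threatens statements about which group scored higher. One that changes over time threatens statements about which group worsened or recovered more, and that is the declared purpose of the models.

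**Working it through.** The documents give no sample size, SD, effect size or diagnostic mix by service, so there is no planned figure to reproduce. What follows is an illustration.

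**Inputs from the documents.** Three services; three time points (T0, T1, T2) for most scales; two (T1, T2) for CGI improvement and IES-R; fixed effects of time and diagnosis.

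**Assumed inputs.** Service offsets of 0, s/2 and s, with s from 0.2 to 0.5 SD. Service mixes for two diagnoses A and B:
- equal: one third in each service for both;
- moderate imbalance: A 40/35/25%, B 25/35/40%;
- strong imbalance: A 60/25/15%, B 15/25/60%.

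**Formula.** Bias in A versus B = sum over services of (service share in A − service share in B) × service offset. The relevant quantity is how each diagnosis is spread over services, not a diagnosis's share within each service.

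**Results (absolute values).**
- Equal mix: all differences in share are 0, so the bias is 0.
- Moderate: the differences are 0.15, 0 and −0.15, so the bias is 0.15 × s. This gives 0.15 × 0.2 = 0.03 and 0.15 × 0.5 = 0.075 SD.
- Strong: the differences are 0.45, 0 and −0.45, so the bias is 0.45 × s. This gives 0.45 × 0.2 = 0.09 and 0.45 × 0.5 = 0.225 SD.

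**Where the bias falls.**
- Offset the same at T0, T1 and T2: the full amount falls on the level contrast. In the change from T0 it is subtracted from itself, leaving 0.
- Offset absent at T0 and present at T1 and T2: the full amount falls on the change from T0. The contrast averaged over three times carries two thirds of it: 2/3 × 0.03 = 0.02 up to 2/3 × 0.225 = 0.15 SD.
- CGI improvement and IES-R: without a T0 value, an offset equal at T1 and T2 cannot be removed from the level contrasts. It still cancels from the T1-to-T2 change.

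**Simulation check.** 20,000 patients per diagnosis, three times, total SD 1, no true diagnosis effect, strong imbalance, s = 0.5, ordinary least squares:

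| Offset | Contrast | No service term | Service added | Service and service-by-time added |
|---|---|---|---|---|
| Stable | Diagnosis main effect (time + diagnosis model) | 0.229 | −0.001 | not run |
| Stable | Time-by-diagnosis at T1, T2 | −0.004, −0.007 | −0.004, −0.007 | −0.006, −0.009 |
| From T1 on | Diagnosis main effect (time + diagnosis model) | 0.149 | −0.007 | not run |
| From T1 on | Time-by-diagnosis at T1, T2 | 0.233, 0.237 | 0.233, 0.237 | 0.014, 0.011 |

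A service main effect repairs the level contrast but does nothing for a time-varying difference. That needs service-by-time.

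**Degrees of freedom.** Service: 3 − 1 = 2. Service-by-time: 2 × (3 − 1) = 4 with three time points, 2 × (2 − 1) = 2 with two. Maximum: 2 + 4 = 6.

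**The case against.** The strongest reply is that the stated aim concerns change, and a stable difference in rating practice cancels from change. That is correct, and it removes half of the worry for the declared target. It does not remove all of it. The model sentence names no time-by-diagnosis term, so the only diagnostic contrast in the model as written is the main effect, which a stable offset does bias. CGI improvement and IES-R, both primary outcomes, have no T0 value, and for CGI improvement the level is itself a rating of change. A time-varying service difference would still bias change.

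A second reply is that no such difference is documented. The services belong to one organisation, and the time points are common calendar periods. This also stands: a reader might infer that service differences are in fact mixed into the diagnostic results, but the documents report neither a difference in mix nor a difference between services.

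Third, a reader might assume that service is already in the dataset. Patients were recruited by service, so it should be retrievable, but Assessment does not list it among the variables.

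Fourth, the sentence on AIC leaves open that other models were tried. With no candidates listed, it cannot be read as adjustment for service, and AIC judges fit rather than control of confounding.

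Finally, not every model is affected. PANSS, YMRS and Y-BOCS are each collected in one diagnosis, so there is no diagnostic contrast to confound. HC belong to no service.

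**Conclusion.** The point holds as a gap in the analysis: three services, a model without service, and a non-randomised comparison of diagnoses leave confounding by service possible and unexamined. The possible bias runs from zero with equal mix to roughly 0.03–0.23 SD under the assumed imbalances and an assumed 0.2–0.5 SD gap between the extreme services. For a stable offset this applies to level contrasts. For an offset arising after T0 it applies to the change from T0, with two thirds of it on the three-time average. These ranges rest on assumed mixes and offsets and are not bounds.

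Two stronger readings are not supported: that the diagnostic contrasts are known to be confounded, and that differing rating practice by itself distorts the comparison of change. The absence of a named time-by-diagnosis term is a separate matter that bears more directly on the aim. Adding service terms would not cure it.

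**What to change.** 1. Retrieve the recruiting service for each patient and tabulate diagnosis by service. If the mix is equal, the concern falls away.
2. Add service as a fixed effect (2 df) in the patient models that compare diagnoses: BPRS, CGI severity and improvement, HAM-A, IES-R among patients, DISS, and HAM-D and MADRS (MDD versus BD).
3. Add service-by-time, at least as a sensitivity analysis for the change contrasts: 4 df with three time points, 2 df for CGI improvement and IES-R. These change contrasts require a time-by-diagnosis term in the same model.
4. Leave PANSS, YMRS, Y-BOCS and the patient–HC contrast for IES-R outside this change.

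Possible wording: *Models comparing diagnostic groups among patients include recruiting service as a fixed effect. Contrasts of change are repeated with a service-by-time interaction. The distribution of diagnoses by service is reported.*

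Cost: up to 6 df, which matters most where groups are small (the documents give no group sizes); a return to the records for service; and rerunning the models, since the plan is written in the past tense and the analyses appear to have been done. No new patient assessment is needed.

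### The time-by-group term that answers the study's question is not in the stated model, and an AIC step with no stated target leaves open whether it was fitted

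*Combined protocol and SAP*

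**What the plan says.** All of this stands in the Statistical Analysis Plan of the combined document, in the paragraph on the regression models.

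- The aim is to "examine whether the change over time in psychometric scores differed between diagnostic groups and, for IES-R, between patients and HC".
- The mean structure is then given: "The model included fixed effects of time and diagnosis". No time-by-diagnosis term is named, and no patient-versus-HC factor is named for IES-R.
- The next sentence is "The Akaike information criterion (AIC) was used to select the appropriate statistical model".
- The sentence after that is "The unstructured variance-covariance matrix was used to account for repeated measures within each subject".
- The significance level is 0.05.

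The plan does not list the candidate models, say what AIC was choosing, state the estimator (ML or REML), or say what is reported if the chosen model has no interaction.

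**The concern.** A difference between groups in change over time is the time-by-group interaction. A model with only main effects of time and group forces all groups to follow parallel profiles, so no parameter in it addresses the stated aim. The sentence describing the mean model omits that term, and the sentence after it hands the choice of model to AIC.

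That leaves two possibilities if the text is followed literally. In the first, the interaction is never fitted and the question is not answered for any scale. In the second, AIC was used on fixed effects, and whether the interaction was fitted depended on each scale's own data. Scales on which it was dropped would then carry no estimate or interval for the quantity of interest. A reader of the results could not tell a term that was tested and found non-significant from one that was never tested.

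**Working it through.** **The plan's own figure.** The only figure on this point is the 0.05 level. It is a chosen setting, and the plan gives no sample size, power or effect size, so there is nothing to reproduce. What can be checked is what the stated model leaves out, and what AIC would do if it decided on the missing term.

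**Inputs.** The Statistical Analysis Plan defines five diagnostic groups. The Primary and Secondary outcomes lists give three time points for most scales (for example "Brief Psychiatry Rating Scale (BPRS) at T0, T1, T2"; likewise CGI severity, HAM-A and DISS). CGI has its "improvement subscale at T1 and T2" only. IES-R is at two times, in patients and HC. HAM-D and MADRS are collected in two diagnoses at three times. PANSS, YMRS and Y-BOCS are each collected in one diagnosis, so they have no between-group term.

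**Step 1: what a main-effects model omits.** With g groups and t times there are g × t means. Main effects use 1 + (g − 1) + (t − 1) parameters. The remainder, k = (g − 1)(t − 1), is the interaction. For five groups and three times: 15 means, 1 + 4 + 2 = 7 parameters, 15 − 7 = 8 omitted. Those 8 are the study's question.

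**Step 2: the cut-off if AIC decides.** Under ML, adding k parameters lowers AIC when the likelihood-ratio statistic exceeds 2k. The implied asymptotic cut-off is P(χ²_k > 2k).

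| Scale | g × t | k | AIC needs LR above | Implied p cut-off | LR needed at 0.05 |
|---|---|---|---|---|---|
| BPRS, CGI severity, HAM-A, DISS | 5 × 3 | 8 | 16 | 0.042 | 15.51 |
| IES-R, five diagnoses plus HC | 6 × 2 | 5 | 10 | 0.075 | 11.07 |
| CGI improvement | 5 × 2 | 4 | 8 | 0.092 | 9.49 |
| HAM-D, MADRS | 2 × 3 | 2 | 4 | 0.135 | 5.99 |
| IES-R, patients versus HC | 2 × 2 | 1 | 2 | 0.157 | 3.84 |

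**Step 3: if p < 0.05 is still required after selection.** The stricter hurdle governs. At 1 to 5 df it is the 0.05 test, so the asymptotic threshold stays at 0.05. At 8 df it is AIC, and the threshold becomes 0.042.

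**Step 4: power.** Take a true interaction that a plain 0.05 test finds with 80% power. At 8 df the noncentrality is 15.02 and P(noncentral χ²_8 > 16) = 0.780. The cost is 80% − 78% = 2 percentage points. At 4 df AIC keeps such a term 86.7% of the time and at 1 df 91.7%. Both exceed 80%, so the 0.05 test remains the binding step and no power is lost.

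**Step 5: non-reporting.** With no true interaction, AIC drops the 8-df term in about 1 − 0.042 = 95.8% of cases and the 1-df term in about 1 − 0.157 = 84.3%. The main consequence is that the interaction estimate goes unreported.

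**Step 6: small-sample check.** With group sizes assumed, complete data and unstructured covariance, simulated retention under no interaction was 0.069, 0.056 and 0.050 at 10, 20 and 40 per group for 8 df. For 1 df it was 0.170 and 0.160 at 25 and 50 per group. The asymptotic values are therefore slightly low, and for the 8-df scales retention is at or a little above 0.05.

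**REML.** Steps 2 to 6 assume ML. Under REML, AIC is not comparable between models with different fixed effects. No percentage is offered for that case, because it would depend on factor coding, group size and SD, none of which the plan gives.

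**The case against.** The strongest reply is that the plan never says AIC was applied to fixed effects. The sentence after it reports an unstructured covariance, and the document is in the past tense. A natural reading is that AIC compared covariance structures and the next sentence gives the result. The listing of time and diagnosis may also be shorthand for a model with their interaction, given the aim stated just before. On that reading nothing is wrong with the analysis, only with its description.

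The first part stands: if AIC chose only the covariance, that step is harmless. The second part is possible but is not on the page. The interaction remains unnamed whichever way AIC was used.

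A reader might also infer two stronger things. One is that the data did decide whether the question was tested. The text permits this but does not state it. The other is that the scales were judged at hidden thresholds up to 0.157 in place of 0.05. That would follow only if being kept by AIC were itself read as the finding. The plan sets 0.05 as its level, and if that test still applies, the threshold does not rise above 0.05 asymptotically on any scale. It would likewise mislead to say that AIC drops 22% of well-powered 8-df interactions without adding that a plain 0.05 test misses 20% of the same ones.

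**Conclusion.** The point holds as a gap in specification. The plan states an interaction question, describes a model without the interaction, and adds a selection step whose target, candidates and estimator are not given. The consequence is that the study's question may go untested on some or all multi-group scales, and the reader cannot tell which. Error inflation is not shown. Under ML, with 0.05 still required, the threshold is 0.05 at 1 to 5 df and 0.042 at 8 df, and the 8-df power cost is about 2 percentage points.

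The numerical results rest on AIC having been used on fixed effects, on ML, and on large-sample approximations. The omission of the interaction from the stated model rests on none of these. The concern covers scales measured in more than one group and does not extend to PANSS, YMRS or Y-BOCS.

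**What to change.** - For every scale measured in more than one group, state that the model always contains time, group and time-by-group, with no selection on fixed effects, and that the interaction is tested at 0.05 and reported whatever its result. For IES-R, say whether group means patients versus HC (1 df) or five diagnoses plus HC (5 df).
- Limit AIC to a listed set of covariance structures compared under that one mean model with REML, or delete the sentence, since an unstructured matrix is already stated. Name the estimator.
- Because the text describes work already done, report which models were compared and on which scales.

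The cost is a few sentences in the plan. A re-run is needed only if the interaction was omitted or was chosen by AIC. The downside is that some non-significant interactions will be reported that would otherwise not have appeared.

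### Five unranked primary scores and an IES-R comparison with HC share one p<0.05 with no multiplicity rule, and the stated model terms do not test differential change

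*Combined protocol and SAP*

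**What the plan says.** Under Primary outcomes the protocol lists four scales that yield five scores, none placed first. BPRS and HAM-A are each scored at all three time points, and IES-R at the last two. CGI supplies two of the five scores: "Clinical Global Impression (CGI) severity subscale at T0, T1, T2; improvement subscale at T1 and T2". Patients are rated on all of them. HC contribute to IES-R only: "HC were asked to retrospectively fill in the IES-R items referring to T1 and T2".

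The Statistical Analysis Plan section sets the grouping: "Patients were divided into 5 groups according to diagnosis (SKZ, BD, MDD, anxiety disorders or OCD, PDs". It gives the aim of the repeated-measures models as being to "examine whether the change over time in psychometric scores differed between diagnostic groups and, for IES-R, between patients and HC". It then describes their content: "The model included fixed effects of time and diagnosis". AIC is named for model selection, but the candidate models are not listed. The only decision rule is "The significance was set at $p < 0.05".

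No section states a multiplicity adjustment, an order of testing, a requirement that all scores succeed, or an exploratory label. MANOVA is named for comparing groups on quantitative variables, but nothing makes it a gate for the repeated-measures models.

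**The concern.** There are two linked gaps.

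**The primary test is not defined.** The question is whether groups changed differently, but the listed terms are main effects. A model with those terms alone assumes equal change in every group, so it cannot answer the question.

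**No rule joins the primary results.** As written, any one of about six tests below 0.05 could be reported as a primary finding. The 0.05 is then the error rate of each test, not of the set of results carrying the primary label. The study is observational and retrospective, so what is at stake is how results are interpreted and reported.

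The first gap has to be closed before the second, because a family of tests cannot be controlled until its members are named.

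**Working it through.** The plan gives no family-wise error figure, so there is nothing to reproduce.

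**Inputs from the documents.** Threshold 0.05; five primary scores; five diagnostic groups; three time points for BPRS, CGI severity and HAM-A; two for CGI improvement and IES-R; one further IES-R comparison, patients against HC.

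**Inputs that are assumptions.** One test per comparison, and the correlation between scores.

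**1. What the named terms test.** Write the mean score in group g at time t as m + a(g) + b(t). The change from t to t' in group g is b(t') − b(t), which does not involve g. The difference in change between any two groups is therefore zero by construction. Differential change needs the group-by-time term.

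**2. Count.** 5 scores + 1 HC comparison = 6 tests.

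**3. Independent tests, no group differing.** 1 − 0.95^6 = 1 − 0.7351 = 26.5%.

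**4. Bound under any dependence.** 6 × 0.05 = 30%.

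**5. Correlated scores.** The interaction degrees of freedom are (groups − 1) × (times − 1):
- three-time-point scores: 4 × 2 = 8
- CGI improvement and IES-R: 4 × 1 = 4
- HC comparison: 1 × 1 = 1

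Simulation with 400,000 draws, using a common correlation between scores, gives the chance of at least one false positive. The two omnibus rows take the HC test as independent of the others; the last row correlates all six tests.

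| Structure of the six tests | Correlation 0.5 | 0.8 | 0.9 |
|---|---|---|---|
| Omnibus, 8 or 4 df as above, plus HC test | 23.7% | 19.2% | 17.0% |
| Omnibus, 4 df for all five scores, plus HC test | 23.0% | 17.7% | 15.1% |
| Six equally correlated two-sided z tests | 20.7% | 13.8% | 10.8% |

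**6. A larger family.** If time and diagnosis main effects were each tested in five models, that is 10 tests. For independent tests, 1 − 0.95^10 = 40.1%.

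**7. With Holm on six tests.** The first threshold is 0.05/6 = 0.0083. The same omnibus simulations give 4.9% (independent), 4.5-4.6% (correlation 0.5) and 2.9-3.3% (0.9).

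**The case against.** **The error rate depends on things the plan does not state.** This stands. Neither the number of tests nor any correlation is in the documents. A reader might take 15% as a floor. It is not: it needs a correlation of 0.9 and 4 df for every score, and single z tests at 0.9 give about 11%. Given six tests, only the 26.5% and the 30% bound need no assumed correlation.

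**The interaction may have been fitted.** A reader might infer that the sponsor tested main effects only. The documents do not show this. The sentence on fixed effects may be shorthand, and AIC may have been used to choose among models that included an interaction. What can be said is that the named terms do not test the stated question.

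**HC could be one more level in a single IES-R model, leaving five tests.** The family would then look smaller (1 − 0.95^5 = 22.6%, first threshold 0.05/5 = 0.01). But a significant omnibus test across diagnoses and HC would not show that patients differ from HC, which is a comparison the SAP names. That still needs its own contrast, so the count returns to six.

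**MANOVA already handles several outcomes together.** It might if it were a gate, but the SAP does not make it one.

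**A retrospective observational study needs no formal error control.** This stands in part. No document says that one significant score makes the study positive, and an exploratory label would be an adequate answer. But the plan uses primary and secondary labels with a significance threshold and gives no such label.

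**Conclusion.** The point holds in a limited form. Five unranked primary scores and one HC comparison are judged at 0.05 with no rule joining them, and the model terms as written do not test whether groups changed differently.

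On the assumption of six tests with no group differing, the chance of at least one false-positive primary result is 26.5% under independence and cannot exceed 30%. It falls with correlation, to 15-17% (omnibus tests) or about 11% (z tests) at 0.9. In every case examined it is at least twice the nominal 5%. Separate tests of main effects would raise it.

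The documents do not support reading this as a known error rate for the study, or as evidence that any reported result is false. Because the SAP is written in the past tense, the analyses may already have been run. A rule added now would guard interpretation but would not restore prespecified error control.

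**What to change.** 1. **Define the primary test.** Include the diagnosis-by-time interaction in each primary-score model and make it the primary test. For IES-R, add a patients-versus-HC by time interaction or contrast. CGI improvement exists only at T1 and T2 and itself rates change, so state whether its test is the group effect or the interaction. Either has 4 df among the five diagnostic groups, so the count does not change.

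2. **Define the family and the rule.** Treat the six tests as the primary family and apply Holm at 0.05 (first threshold 0.0083). Report adjusted beside unadjusted p-values, claim a primary finding only when the adjusted p is below 0.05, and describe the rest as exploratory. If HC is a level in a single IES-R model, the patients-versus-HC contrast still counts as its own test. Naming one lead comparison, or labelling all results exploratory, is an acceptable equivalent.

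3. **Place the MANOVAs.** State that they are descriptive and outside the family.

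4. **Disclose timing.** If the analyses have been run, say that the rule is post hoc.

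**Cost.** No new data. A few sentences, one column of adjusted p-values and, if only main effects were fitted, up to six refits on existing data. The downside is that isolated borderline results on a single scale can no longer be claimed as primary findings.
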